The treatment will be discontinued if the patient develops an adverse event (discussed under *6. Safety Management*) that requires the treatment to be stopped or at the participant request. Subjects will be allowed to start and continue conventional medical therapy for the duration of the study, including any pain medications. This will be at the discretion of the treating physician. This will allow us to assess the addition of TEA to conventional care. The TEA intervention will be discontinued if the patient gets admitted to hospital or if a surgical or endoscopic procedure is performed during the treatment phase of the study. During the 4 weeks of treatment, subjects will complete pain diaries through RedCap. This will take 2 minutes for completion.

IV. Monitoring phone calls

To assess any potential problems with the TEA device, we will contact participants via telephone within 72 hours of starting treatment and then weekly at 1 week, 2 weeks, and 3 weeks from treatment initiation.

V. Visit 2 (V2), 4 Weeks from V1

During this follow-up period subjects will complete the same set of surveys that was completed during the first visit to assess pain, quality of life, and anxiety or depression. Subjects will also return the TEA device using their return mailer (provided during or prior to visit 1). In the event the device is broken or non-functional, participants will still be requested to return the device.

VI. Visit 3 (V3), at 8 weeks from V1

After subjects finish treatment (4 weeks from V1), they will continue completing daily pain diaries for additional 4 weeks. During this phase, subjects will not receive device stimulation. At 8 weeks from V1, subjects will be asked to complete the same set of surveys completed during visit 1 and 2. These will be completed via RedCap.

VII. Close-out phone call, at end of trial

At the end of the trial, study subjects who enrolled and received TEA will be reached out via a phone call to assess on global impression and acceptability of the treatment.

Outcomes

Primary outcomes

1. Enrollment feasibility: how many patients with CP who are assessed meet eligibility criteria. In addition, of these, how many provide informed consent. Of those who consent, how many meet criteria to participate after the run-in period. Of those who meet run-in period criteria, how many start the intervention (TEA).

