8. Rates of hospital admission for pancreatitis-related hospital admissions [timeframe – 8 weeks from treatment onset]
9. Rates of treatment-related adverse events [timeframe - 4 weeks from treatment onset]
10. Patient global impression of change (PGIC) [timeframe: end of follow-up]: this is a 1-item question that should take less than 1 minute to complete. This question assesses the overall change on pain by using a 7-point Likert scale that ranges from (1) very much improved to (7) very much worse.
11. Modified abbreviated acceptability rating profile [timeframe: end of follow-up]: this is an 8-item questionnaire that should take 2 minutes (Tarnowski KJ, Simonian SJ. Assessing treatment acceptance: the Abbreviated Acceptability Rating Profile. *J Behav Ther Exp Psychiatry* 1992;23:101-6). Each item uses a 5-point Likert scale, including Strongly disagree, Disagree, Neutral, Agree, and Strongly agree. A final score ranges from 0-40, with 40 indicating the highest acceptability possible. This will serve to assess how study subjects perceive the acceptability of the TEA treatment for pain in CP.

Participant timeline

After enrollment, participants will have a 2-week run-in period, where they will complete daily pain diaries. If participants fulfill minimal pain requirements, participants will complete V1 to provide baseline data and will start TEA treatment. Participants will undergo TEA therapy twice a day for 4 weeks. During that time, participants will continue completing daily pain diaries and will 3 weekly phone calls to assess adverse events. After 4 weeks of TEA therapy, the participants will return the device and will complete V2, in which participants will complete questionnaires similar to V1. Participants will then continue completing daily pain diaries for additional 4 weeks, while not receiving the TEA therapy. At completion of those 4 weeks, participants will have closure V3, in which they will provide questionnaires similar to V1 and V2. The total participant's duration in the study is 10 weeks (2 weeks run-in, 4 weeks TEA treatment, and 4 weeks post TEA treatment assessment). At the end of the trial, participants will receive a close-out phone call to assess treatment acceptability.

Table 2: schedule of study visits

Visit ID	V0	V1	Phone call 1	Phone call 2	Phone call 3	Phone call 4	V2	V3 ^	Close-out
Target time	- 2 weeks	0	Within 72h	+1w	+2w	+3w	+4 weeks	+8 weeks	End of trial
Time window	2 weeks	+ 1 week					+ 1 week	+ 1 week	

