All data will be collected using active and passive methods, including patient interviews, physical examinations, and review of electronic medical records. A trained research coordinator will collect data using standardized forms via RedCap. Research coordinators will follow the manual of operations for all study procedures. All forms will include essential instructions and definitions of variables.

A. Pre-screening form: this will include questions on inclusion and exclusion criteria, pertinent for study eligibility. Initial screening will be based on chart review, in person or telephone patient interview, endoscopic results, and radiologic data that are consistent with the study definition of CP. Screening data will be obtained by the research coordinator before enrollment. This is uploaded into section 8-1.8

B. Pain diary: this will be directly completed by patients. Daily pain scores will be recorded during the 2-week run in period. In those patients who are eligible and are started in TEA, patients will complete the pain diary for 4 weeks during the TEA therapy and will continue for 4 weeks after the intervention is over. The patients will report (a) average pain during the last 24 hours using a VAS, (b) maximal pain during the last 24 hours using a VAS, and (c) weekly BPI-SF (only after intervention started). The survey is uploaded into section 29.1.

C. Baseline form: this will include data on demographics, clinical profile of CP, laboratory biomarkers, radiologic findings, and prior therapeutic interventions, all of which will be recorded from the medical records and by patients filling up a survey. In addition, patients will complete a form pertaining to pain, quality of life, anxiety and depression using the instruments described in secondary outcomes.

D. First follow-up form: this form will be used to assess pain, quality of life, anxiety and depression after the intervention, using the instruments described in secondary outcomes. Adverse events of the intervention will also be recorded in this form. These surveys are uploaded into section 29.1.

E. Second follow-up form: This form will be given to participants during the first follow-up (V2). Subjects will be asked to complete and mail the follow-up questionnaires and diary. This form will be used to assess pain, quality of life, anxiety and depression after the intervention has been discontinued. These surveys are uploaded into section 29.1.

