All data will then be captured in a password-protected database through Redcap. Several methods will be used to promote data quality and integrity including database development, proper training of study team members, and use of data quality rules and validation. Each subject will be assigned a unique random number, and Protected Health Information will be coded to

ensure no one outside the study team will be able to identify a subject's identity. This database will be stored in a password-protected database, in a password-protected folder on a secure server behind the University of Michigan firewall. The information will, at all times, only be able to be accessed by the study investigators.

F. After enrollment is completed, study subjects who enrolled and received TEA will be reached out via a phone call to assess on global impression and acceptability of the treatment. Study subjects will be asked the following questions in relation to the use of TEA on their chronic pancreatitis pain.

- Patient global impression of change (PGIC): this is a 1-item question that should take less than 1 minute
- Modified abbreviated acceptability rating profile: this is an 8-item questionnaire that should take 2 minutes (Tarnowski KJ, Simonian SJ. Assessing treatment acceptance: the Abbreviated Acceptability Rating Profile. *J Behav Ther Exp Psychiatry* 1992;23:101-6).
- Two open questions: (i)“How did the TEA device help you in managing your pancreatitis pain?” and (ii)“What modifications would you suggest to improve the TEA treatment?”

5. Statistical methods

Sample size calculation

We will conduct an open-label pilot study of 10 subjects with CP that fulfill eligibility criteria and that receive the TEA device during visit 1. This will serve to inform feasibility on enrollment, adherence, retention, and completion of data collection. Data obtained in this study will lead to protocol changes for a larger randomized controlled trial that we will plan in the future. The study will be under powered to address any clinical outcomes. We anticipate attrition of approximately 10% for a study of this nature.

Statistical analysis

All analyses will be performed according to the intention-to-treat principle. All primary outcomes will be measured using descriptive statistics as absolute values (percentage), mean \pm standard deviation (SD), and median (interquartile range [IQR]), as appropriate.

Primary outcomes

A. Enrollment feasibility:

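### PGIC and acceptability are listed for the end of follow-up but collected in an end-of-trial call that nothing ties to each participant's own V3

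*Combined protocol and SAP*

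**What the plan says.** All places are in the combined protocol and SAP.

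- **Exploratory outcomes, items 10 and 11:** "Patient global impression of change (PGIC) [timeframe: end of follow-up" and "Modified abbreviated acceptability rating profile [timeframe: end of follow-up".
- **Section 3, VII (close-out phone call):** "At the end of the trial, study subjects who enrolled and received TEA will be reached out via a phone call".
- **Participant timeline:** V3 is described first, as the closure visit. Then: "At the end of the trial, participants will receive a close-out phone call to assess treatment acceptability".
- **Table 2:** neither instrument is ticked at V3. Both are ticked only in a separate close-out column, to the right of V3, whose target time is the end of the trial. V1, V2 and V3 each carry a window of + 1 week; the close-out column has none.
- **Section 3, VI (V3):** "At 8 weeks from V1, subjects will be asked to complete the same set of surveys completed during visit 1 and 2". PGIC and acceptability are not in that set.
- **Section 4, item F:** "After enrollment is completed, study subjects who enrolled and received TEA will be reached out via a phone call to assess on global impression".
- **Section 5, exploratory endpoints:** COMPAT-SF, opioid use and dose, quality of life and HADS are analysed at the end of follow-up without treatment, which is given as 8 weeks. PGIC and acceptability are each summarised as one proportion, with no mention of when the rating was made.

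**The concern.** For a participant, follow-up ends at V3. The outcome list therefore points to week 8, while the procedures point to a contact defined by the progress of the trial as a whole. Item F adds a second trial-level trigger, the completion of enrollment, which on its own sets only an earliest time.

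Both instruments ask the participant to look back. If everyone is called on one date, the first person treated looks back much further than the last, and the two proportions pool ratings made at very different distances from treatment. Conventional therapy, including pain medication, may start or change during the study, so a late rating of overall change may also reflect care received after TEA stopped. No rating date or interval is planned for reporting, so a reader could not see this. The pilot is meant to shape a larger randomized trial, and acceptability bears directly on that.

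**Working it through.** **The plan's own figure.** Run-in 2 weeks + treatment 4 + post-treatment 4 = 10 weeks, the total participant duration stated in the participant timeline. V3 uses up all of it, so a contact after V3 lies outside the stated duration.

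**Inputs from the documents.** 10 treated participants (sample size section); TEA for 4 weeks from V1, ignoring the one-day delay after training; V3 at 8 weeks from V1, window + 1 week (Table 2); study to be completed in 12 months (section 8), taken as 52 weeks.

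**Assumptions.** Accrual is not stated, so the span E from first to last V1 is varied. The 10 entries are evenly spaced, all complete 4 weeks of TEA, and everyone is called on one date, at the last participant's V3.

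**Formula.** The first V1 is at week 2 and the last at week 2 + E, so the call is at week C = 2 + E + 8. For participant k = 0, ..., 9, V1 is at week 2 + kE/9, and

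lag from last stimulation = C - (V1 + 4) = 4 + E(9 - k)/9.

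The range is 4 to 4 + E and the median is 4 + E/2. The longest case fits the 12 months exactly: 2 + 42 + 8 = 52.

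| Entry span E | Call at week | Lags in order of entry (weeks) | Median | Over 9 weeks |
|---|---|---|---|---|
| 42 weeks | 52 | 46, 41.3, 36.7, 32, 27.3, 22.7, 18, 13.3, 8.7, 4 | 25 | 8 of 10 |
| 21 weeks | 31 | 25, 22.7, 20.3, 18, 15.7, 13.3, 11, 8.7, 6.3, 4 | 14.5 | 7 of 10 |
| 8 weeks | 18 | 12, 11.1, 10.2, 9.3, 8.4, 7.6, 6.7, 5.8, 4.9, 4 | 8 | 4 of 10 |

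With one call date, the difference in lag between two completers equals the gap between their V1 dates. That is why the lag follows entry order.

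**Comparison at V3.** A completer rated at V3 has a lag of 8 - 4 = 4 to 9 - 4 = 5 weeks, whatever the accrual. Someone who stopped at the end of week 1 would have 8 - 1 = 7 to 9 - 1 = 8 weeks.

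**The case against.** The mismatch can be read as a loose label. Among the exploratory outcomes, those assessed out to week 8 say so in weeks from treatment onset; only these two use the end-of-follow-up label, and they are also the only two placed in the close-out column. The authors may have meant a different contact. Against this, the analysis section uses the same label for week 8, so the label remains ambiguous.

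The end of the trial could mean the end of each person's participation, since it appears in a per-participant timeline and schedule. That reading is open. The separate column after V3, the naming of V3 as the closure visit and item F's reference to enrollment all favour the trial-level one.

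The blank window is weak evidence by itself. As extracted, Table 2 gives phone calls 1 to 4 no window entry either, although those calls do have target times counted from the participant's own start of treatment. A manual of operations, not available here, may settle the timing. What stands is that no text in the document does.

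The longest lags need slow entry. Section 8 reports roughly 104 new patients and 203 return visits a year, with 87% expected to have chronic abdominal pain, so faster entry is possible; the 8-week case is included for that reason. All the figures measure lag. None shows a change in either proportion.

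**Conclusion.** The concern holds as a minor one. The timing statements disagree, and none ties the call to the participant's own V3. Under the stated assumptions, one call date gives lags of 4-46, 4-25 or 4-12 weeks for entry over 42, 21 or 8 weeks, against 4-5 weeks for completers rated at V3. If each call follows the participant's V3, there is no problem.

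Three stronger conclusions are tempting and are not supported:

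- **That the plan fixes one call date for everyone.** It does not say so; that is only the more natural reading.
- **That a primary outcome is compromised.** Data collection feasibility does not say whether the close-out forms count among the surveys, so it cannot be claimed that they are impossible to score as completed per protocol. Retention refers to week-8 questionnaires, and Table 2 does not list these two forms at V3.
- **That 46 weeks is the expected lag.** It is the top of a range resting on assumed accrual that fills the whole 12 months.

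The effect is confined to two exploratory descriptive proportions in 10 participants, in a study that declares itself underpowered for clinical outcomes. The pain diary, BPI-SF and COMPAT-SF have their own scheduled times and are unaffected.

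**What to change.** Make the close-out call for PGIC and acceptability within a stated window after each participant's own V3, for example the + 1 week that V3 already has. Bring section 3 VII, the participant timeline, the close-out column of Table 2 and section 4 item F into line with the outcome list. Record the date of each rating, so that the interval from last stimulation can be seen, including for anyone who stopped early.

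With that example window, a completer would be rated between 8 - 4 = 4 and 9 + 1 - 4 = 6 weeks after the last stimulation, whatever the accrual.

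The cost is wording in four places, one recorded date and up to 10 individually scheduled calls instead of one batch. The phone mode and the week-8 survey set do not change, and the two open questions can stay in the same call.

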Approach: We propose to conduct an open-label feasibility trial to understand the feasibility of TEA in patients with painful CP. In this open-label study, all subjects will receive TEA at acupoint ST36 in an unblinded manner. This will inform on recruitment & retention rates, percentage of patients with complete data collection and compliance with study procedures. This will also assist in sample size calculations for a future larger study.

Aim 2: To collect pilot data on the efficacy of TEA on abdominal pain, patient reported outcomes, and quality of life, in patients with painful CP. TEA at ST36 has been shown to be effective in the treatment of patients with abdominal pain due to visceral hypersensitivity and pancreatic inflammation.^{10, 15} We will use parameter P100 (100Hz, 0.5ms, 0.1s-on and 0.4s-off, and tolerable current output), which has been found most effective in treating visceral pain in animals and patients with irritable bowel syndrome.^{13, 16} TEA at this acupoint may be effective in ameliorating pain in CP by improving pancreatic inflammation or autonomic function.

3. Methods: participants, interventions, and outcomes

In this study, we aim to assess feasibility of TEA, enrollment methods, and data collection tools. All patients will receive TEA via ST36 twice daily (a point below the knee cap) in an unblinded fashion. We will then use this preliminary data to apply for competitive funding to conduct a larger study. The population, intervention and outcome for this study are summarized in **Table 1**.

Table 1: Summary of study population, interventions, outcomes and setting

Population	Adult subjects aged 18 to 75 years with chronic pancreatitis and abdominal pain
Intervention	Home-based 30-minute sessions of TEA twice a day for 4 weeks
Control	None
Outcome	Enrollment, retention, and data collection feasibility
Setting	Comprehensive pancreas clinic at the University of Michigan

Eligibility criteria:

Inclusion criteria

1. Age 18 to 75 years of age.
2. Diagnosis of chronic pancreatitis, based on a score ≥ 4 using the previously validated Mayo scoring system that uses morphologic and functional criteria¹⁷, or endosonographic features suggestive or consistent with CP based on Rosemont criteria¹⁸.
3. Abdominal pain present at least once a week within the last month
4. Willing and able to provide written informed consent

Exclusion criteria

1. Pregnancy or breastfeeding mother
2. Imprisoned individuals

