 - Rank-sum test or paired t test depending on data distribution to compare mental QOL from end of follow-up without treatment compared to mental QOL at end of treatment
- Hospital anxiety and depression scale (HADS)
 - Mean \pm SD of HADS score at onset of treatment (at baseline during visit 1)
 - Mean \pm SD of HADS score at end of treatment (at 4 weeks during visit 2)
 - Mean \pm SD of HADS score at end of follow-up without treatment (at 8 weeks)
 - Mean difference of HADS score from end of treatment compared to baseline.
 - Rank-sum test or paired t test depending on data distribution to compare HADS score from end of treatment compared to baseline
 - Mean difference of HADS score at end of follow-up without treatment compared to baseline
 - Rank-sum test or paired t test depending on data distribution to compare HADS score from end of follow-up without treatment compared to baseline
 - Mean difference of HADS score at end of follow-up without treatment compared to HADS score at end of treatment
 - Rank-sum test or paired t test depending on data distribution to compare HADS score from end of follow-up without treatment compared to HADS score at end of treatment
- Pancreatitis related hospitalizations
 - Proportion of patients who had a pancreatitis related hospitalization during the treatment period

- Proportion of patients who had a pancreatitis related hospitalization during the follow up period without treatment
- Proportion of patients who had a pancreatitis related hospitalization during the study period
- Adverse events
 - Proportion of patients who had an adverse event due to the intervention
- Patient Global Impression of Change
 - Proportion of patients who consider their pain improved (PGIC ≤ 3)
- Treatment acceptability
 - Proportion of patients who agree or strongly agree that the treatment was an acceptable intervention for dealing with chronic pancreatitis pain

For missing data, we will use multiple imputation methods. Statistical significance will be defined as $P < 0.05$.

6. Safety management

Safety monitoring

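### One open question in the close-out call presumes benefit, and the two overall ratings of TEA are taken only by phone in an unblinded, uncontrolled study; a minor point with a cheap fix

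*Combined protocol and SAP*

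**What the plan says.** Section 3 (Interventions, VII) and Section 4 (item F) plan a telephone call to every subject who received TEA, who "will be reached out via a phone call to assess on global impression and acceptability of the treatment". Item F places it late: "After enrollment is completed, study subjects who enrolled and received TEA" are the people called.

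Item F lists the content in this order: the PGIC, the acceptability profile, then two open questions. The first open question is "How did the TEA device help you in managing your pancreatitis pain". The second is "What modifications would you suggest to improve the TEA treatment".

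The design gives no masking and no comparator. Section 2, Aim 1, states that "all subjects will receive TEA at acupoint ST36 in an unblinded manner", and Table 1 lists no control.

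Other patient-reported data follow a different route. Patients fill in the pain diary themselves (Section 4, item B). Of the week-8 surveys, Section 3 (VI) says "These will be completed via RedCap".

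In the exploratory endpoints of Section 5, the PGIC is summarised as "Proportion of patients who consider their pain improved", defined as a score of 3 or less. Acceptability is summarised as the proportion in the top two agreement categories. Neither is tested.

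**The concern.** Two features of the call matter, and they are separate.

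- **Wording.** The first open question asks how the device helped, not whether it did. A patient who noticed no effect, or felt worse, has to contradict the premise to answer honestly.
- **Mode.** The PGIC and the acceptability profile are the two instruments in which patients judge the treatment as a whole. They are given to a person on the phone, while symptom and quality-of-life scores are not. In an open-label single-arm study, some patients may give a caller a kinder answer than they would give a form. There is no second arm in which the same tendency would appear and could be compared.

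At stake is how far these two ratings, and the free-text answers, can be trusted when the results are used to plan the larger randomised trial that Section 5 (sample size) describes. Table 2 schedules both ratings at close-out only, so no self-completed version exists to check them against.

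**Working it through.** The plan states no figure on this point that could be reproduced. The check is mainly a comparison of sections, followed by a small sensitivity calculation.

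**1. What is inside the call and what is outside**

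| Item | How collected | Source |
|---|---|---|
| PGIC | Phone, close-out only | Section 3 (VII); Table 2; Section 4, item F |
| Acceptability profile | Phone, close-out only | same |
| Two open questions | Phone, close-out only | Section 4, item F |
| Daily pain diary | Completed by the patient | Section 4, item B |
| Week-8 COMPAT-SF, opioid use, PROMIS-29, HADS | Completed by the patient | Section 3 (VI); Table 2; Section 4, item E |
| Enrollment, adherence, retention, visit duration, survey completion | Study records and device log | Section 3, primary outcomes |

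Section 3 (VI) has the week-8 surveys done in RedCap, while Section 4, item E, has them mailed back. Either way no interviewer is involved, so the contrast with the call holds. Only the first three rows are exposed to the call.

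**2. Whether the leading question can reach the ratings**

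Item F puts the ratings before the open questions. If that order is kept, the leading question cannot affect a rating already given. The order is not stated to be fixed. The rating scales are not one-sided: the PGIC has seven points running from improvement to worsening, and the acceptability items have five points with a neutral middle and two levels of disagreement (Section 3, exploratory outcomes 10 and 11). The wording problem is therefore confined to open question (i), and the mode problem to the two ratings.

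**3. Safeguards stated**

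Neither description of the call says who makes it, or mentions an independent caller or neutral interviewing. Section 4 does say that coordinators are trained, use standardised forms and follow an operations manual. That manual is not among the documents.

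**4. Sensitivity of the two proportions**

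Inputs from Section 5 (sample size): n = 10 and attrition of about 10%, leaving 10 × (1 − 0.10) = 9.

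One patient crossing the cut-off changes the proportion by 1/n:

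- n = 10: 1/10 = 10.0 percentage points
- n = 9: 1/9 = 11.1 percentage points

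Exact (Clopper–Pearson) 95% limits are the 0.025 quantile of Beta(x, n − x + 1) and the 0.975 quantile of Beta(x + 1, n − x). The counts below are illustrative:

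- 7/10 = 70%: 34.8% to 93.3%
- 8/10 = 80%: 44.4% to 97.5%
- 7/9 = 77.8%: 40.0% to 97.2%

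These figures show how coarse the two results will be. They do not measure bias: the same step size applies to every binary result in the study.

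**The case against.** The case for leaving the call as it is has several parts.

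- **The results affected are low in the hierarchy.** The PGIC and acceptability are exploratory and descriptive, the open answers are neither a listed outcome nor in the analysis plan, and the protocol itself says the study is underpowered for clinical outcomes. This stands, and it is why the point is minor.
- **The call leaves room for unfavourable answers.** Both scales include them, and the second open question asks for changes. This stands for the call as a whole. It does not repair question (i): suggesting improvements to a treatment is not the same as reporting no effect or harm.
- **Phone is a normal way to reach people at the end of a trial, and self-completion may lose replies.** With 10 patients one missing reply matters. This is a fair objection to replacing the call, but not to sending a form first and keeping the call for those who do not return it.
- **Interviewer instructions may exist in the operations manual.** They cannot be assumed absent. They would reduce the mode concern but would not change the scripted wording of question (i).

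A reader might also infer more than the documents support: that every patient judgement at the end of the trial leans towards TEA. The week-8 surveys and diaries are completed outside the call. They carry the ordinary limits of an open-label design, but nothing from the call. A reader might likewise assume that the caller is the coordinator who trained the patient. Section 3 gives the device training to the study coordinator and describes several monitoring calls, which makes this plausible, but no section identifies the close-out caller.

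**Conclusion.** The point holds in a narrow form. Open question (i) presumes benefit, on its plain wording. The PGIC and the acceptability profile are at risk of interviewer and social-desirability bias because they are collected only by phone in an unblinded study with no control. That ratings are spoken to the caller is inferred from the use of a phone call.

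This is a risk, not a demonstrated shift. The documents give no evidence on the direction or size of any bias, and the 10-point step per patient should not be read as an estimate of it. The primary feasibility outcomes, the diaries and the week-8 surveys are unaffected by the call. The severity is minor. It is still worth correcting before the calls are made, because answers to a leading question cannot be repaired afterwards.

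**What to change.** 1. Reword open question (i) neutrally, for example: *What effect, if any, good or bad, did the TEA device have on your pancreatitis pain?*
2. State that the open questions always come after the two ratings.
3. Send the PGIC and the acceptability profile as a self-completed RedCap survey before the call. Use the call for the open questions, and for the ratings only when the survey has not been returned.
4. Record the mode of completion for each patient and report it beside the two proportions.

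The cost is one sentence in the script, one form in a system already in use, and matching edits to Section 3 (VII) and Section 4, item F. A small downside is that a reminder may be needed to keep the response rate.
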